9.2. Sample Size Calculation

Primary endpoint: time to bowel transit recovery (quantitative variable). Calculation based on a mean transit recovery time of 48 hours postoperatively. For a 15% reduction (48h to 41h) in the treated group, standard deviation of 20h, alpha risk of 5%, power of 80%, bilateral test: 300 inclusions needed (150 patients per group).

9.3. Significance Level

Bilateral threshold: 0.05

9.7. Analysis Population

Modified intention-to-treat (mITT) population: all randomized patients excluding those who died early without bowel transit recovery (absence of primary endpoint). Each patient will be analyzed in their randomization group. A CONSORT diagram will be provided.

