4. JUDGMENT CRITERIA

4.1. Primary Endpoint

Time (in hours) to bowel transit recovery after cardiac surgery, defined as the duration in hours between the first anesthetic induction and the emission of the first significant stool (approximately 100g as judged by the nursing assistant or nurse in charge of the patient, blinded to treatment).

The number of patients who received macrogol and the number who received picosulfate will be indicated for each arm.

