6.2. Study Conduct

6.2.1. In the Cardiology/Cardiac Surgery Ward:

a) Inclusion: Patients will be informed of the protocol by an investigator physician during the cardiology consultation. Clear and transparent information will be provided orally and in writing. Inclusion and non-inclusion criteria will be verified. Informed consent will be obtained after a reflection period deemed sufficient by the patient.

b) Randomization: Patients will be randomized the day before surgery (1:1) into two groups:

- Naloxegol Group: Interventional arm receiving the experimental treatment 'naloxegol'
- Placebo Group: Comparison arm receiving an inert tablet

Randomization will be performed electronically via the eCRF by a nurse 'outside the protocol' who will administer the treatment according to the randomization group.

6.2.2. In the Operating Room:

Standard management of patients for anesthesia and cardiac surgery.

6.2.3. In the ICU and CCU:

- Standard patient management
- Naloxegol Group: administration of a naloxegol 25mg tablet at 24h postoperatively, then every 24h until bowel transit recovery, maximum 5 days
- Placebo Group: administration of an inert tablet at 24h postoperatively, then every 24h until bowel transit recovery, maximum 5 days
- At Day 2 in absence of bowel transit: administration of macrogol until transit recovery
- At Day 4 in absence of bowel transit: administration of sodium picosulfate (Citrifleet)

6.2.4. In the Ward and at Home:

Collection of patient vital status and possible adverse events daily during hospitalization, then at 1 month by telephone call.

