6.8. Stopping Rules for Individual Participants

Any subject included in the study may withdraw consent at any time for any reason without explanation and without affecting the care provided. Early death without bowel transit recovery (absence of primary endpoint) will lead to exclusion from analysis (mITT). These patients will be replaced to avoid loss of statistical power.

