7. TREATMENTS ADMINISTERED TO RESEARCH PARTICIPANTS

7.1. Investigational Medicinal Product

| | |
|-----------------------|---|
| Trade Name | MOVENTIG® 12.5mg and 25mg film-coated tablets |
| INN | Naloxegol |
| Manufacturer | Piramal Healthcare UK Limited, Morpeth, United Kingdom |
| MAH | Kyowa Kirin Holdings B.V., Hoofddorp, Netherlands. EU centralized MA: December 8, 2014 |
| Dosing Regimen | 12.5mg tablet 2 hours before surgery, then 25mg every 24h after surgery until bowel transit recovery (max 5 days) |
| Placebo | Inert tablet (Arrow). Round white 300mg tablet. Administered under the same conditions as the active treatment. |

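### Excluding and replacing randomised patients who die early without transit recovery conditions the primary comparison on a post-randomisation event tied to the endpoint

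*Combined protocol and SAP*

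**What the plan says.** Section 9.7 (Analysis Population) defines one population, a modified ITT set: "all randomized patients excluding those who died early without bowel transit recovery (absence of primary endpoint"). Patients are analysed in their randomised group and a CONSORT diagram is promised. Section 6.8 (Stopping Rules) states the same rule: "Early death without bowel transit recovery (absence of primary endpoint) will lead to exclusion from analysis (mITT"). It then adds: "These patients will be replaced to avoid loss of statistical power".

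The timing matters. Section 6.2 says "Patients will be randomized the day before surgery (1:1) into two groups", and section 7.1 gives the regimen as "12.5mg tablet 2 hours before surgery, then 25mg every 24h after surgery until bowel transit recovery (max 5 days"). The deaths concerned therefore follow randomisation and, from surgery onward, normally follow the first tablet.

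The primary endpoint (4.1) is "the duration in hours between the first anesthetic induction and the emission of the first significant stool". Section 9.1 plans a t-test or a Wilcoxon-Mann-Whitney test for it, depending on its distribution. The documents contain no analysis of all randomised patients, no competing-event or worst-rank analysis, no sensitivity analysis and no time limit for *early*.

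**The concern.** A patient leaves the analysis on meeting two conditions that arise after randomisation: death, and transit not yet recovered. The second is the primary endpoint still in progress. A patient with a short ileus soon passes out of reach of the rule, while one with a long ileus stays exposed to it. The rule therefore tends to remove slow patients, and may do so unequally in the two arms.

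The protocol does not treat such deaths as certainly unrelated to treatment. Section 8.4 requires immediate notification of gastrointestinal perforation, Ogilvie syndrome, mesenteric ischaemia and any fatal event. If one arm had more deaths of this kind, it would lose some of its slowest patients and look faster, so harm could be read as benefit.

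Replacement does not repair this. Under section 6.7.3 a new patient takes the next number in the sequential list, so need not enter the arm that lost someone. Because *early* is undefined, deciding who is excluded also becomes a judgement made after randomisation.

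**Working it through.** **1. Sample size (is replacement needed for power?).** Section 9.2 gives "For a 15% reduction (48h to 41h) in the treated group", a difference of 7 h (an exact 15% is 0.15 × 48 = 7.2 h), with "standard deviation of 20h, alpha risk of 5%, power of 80%, bilateral test".

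- Normal approximation: n per group = 2(1.960 + 0.842)² × 20² / 7² = 2 × 7.85 × 400 / 49 ≈ 128.1, so 129.
- Exact t-test: 129.1, so 130 per group (260 in total).
- Wilcoxon test, normal data: 129.1 × π/3 ≈ 135.2, so 136 per group (272 in total).
- The stated 150 per group (300) is not reproduced from these inputs alone. It is larger than they require, by 300 − 260 = 40 for the t-test or 300 − 272 = 28 for Wilcoxon.
- Power of the t-test is 85.6% with 150 per group, and 83.6% with 142 per group (about 5% lost).

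**2. Size of the bias by hand.** Assume no drug effect and lognormal times with mean 48 h and SD 20 h. The log-scale SD is √ln(1 + (20/48)²) = √0.160 = 0.400. The mean of the slowest 20% is 48 × Φ(0.400 − 0.842)/0.20 = 48 × 0.329/0.20 ≈ 79 h, about 31 h above the overall mean. If k such naloxegol patients out of 150 are excluded and replaced by average patients, the arm mean falls by about 31k/150:

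- k = 3: 0.6 h
- k = 5: 1.0 h
- k = 8: 1.7 h

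If k is equal in the two arms the shifts cancel. If deaths are unrelated to transit, the excluded patients average 48 h and there is no shift.

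**3. Simulation of the same model.** 150 per arm, 4,000 trials per scenario, Wilcoxon test, exclusion with same-arm replacement. The nominal favourable error is 2.5%.

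| Deaths, naloxegol v placebo | Source | False benefit | Falsely favourable |
|---|---|---|---|
| 3 v 0 | slowest 20% | 0.6 h | about 4.5% |
| 5 v 0 | slowest 20% | 1.0 h | about 5.5% |
| 8 v 0 | slowest 20% | 1.7 h | about 9.5% |
| 3 v 3 | slowest 20% | under 0.1 h | 2.6% |
| 5 v 5 | slowest 20% | under 0.1 h | 3.0% |
| 8 v 0 | unrelated to transit | 0.0 h | 2.3% |

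Repeated runs of the first three rows ranged over 4.1–4.6%, 5.3–6.9% and 9.1–10.1%. When the same deaths were ranked worst instead of excluded, the falsely favourable rate was 2.3% or less.

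**4. Different model.** Normal times, deaths drawn from the slowest 25%, no replacement, t-test, 3,000 trials. Two-sided error was 5.4–5.6% with equal death rates (1% v 1%, 2% v 2%). It was 6.6% at 3% v 1% (naloxegol v placebo) and 8.8% at 5% v 1%, with false benefits of about 0.5 h and 1.0 h. The direction does not depend on replacement or on the choice of test.

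**5. Cost of the alternative.** With no transit effect and 8 v 0 deaths unrelated to transit, worst rank declares naloxegol significantly slower in about 11–12% of trials, against 2.3% with exclusion. With a true 7 h effect and 5 v 2 unrelated deaths, power was 88% with worst rank and 95% with exclusion. A run under other assumptions gave 81% and 90%. The gap is 7 to 9 points in each.

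**The case against.** Material bias needs two things together: an imbalance in deaths, and a link between death and slow transit. The documents show neither. The 3, 5 and 8 v 0 scenarios are worst cases, and even the largest gives 1.7 h against a 7 h target. This stands, and it limits the claim to what could happen.

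The stated objective (3.1) is the duration of ileus. A death from bleeding or infarction, which section 8.4.2 attributes to the surgery, says little about the bowel. Counting it as the worst transit outcome is a choice of estimand that brings mortality into the test. This also stands, and is why worst rank is better as a sensitivity analysis than as the primary analysis.

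Deaths would not be hidden either, given the notification rule in 8.4 and the CONSORT diagram. That is true, but neither corrects the primary test.

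Three stronger readings are tempting but unsupported:

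- A reader might infer that every death before transit recovery is excluded. Both sections say *early*, so the reach of the rule is unknown.
- A reader might infer that naloxegol raises mortality, or that the result will be biased. The documents give no death rate and no evidence of a drug effect on death.
- A reader might infer from the replacement rule that 300 leaves no room for loss. The stated inputs show some margin.

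**Conclusion.** The concern holds in a limited form. The only defined population selects on a post-randomisation event linked to the primary endpoint, and nothing else in the documents repairs this. The bias runs from essentially nil (few balanced deaths, or deaths unrelated to transit) to about 0.6–1.7 h, with the favourable error rising from 2.5% to about 4.5–9.5%, if 3 to 8 excess naloxegol deaths fall among the slowest fifth. Those death counts and the lognormal shape are assumptions; only the mean, SD, target difference and group size come from the plan. Balance cannot be assumed in advance, and the dangerous direction is harm appearing as benefit, so the rule should be changed before unblinding. The power argument for replacement is weak: 150 per group can lose 20 patients for a t-test (150 − 130), or 14 for Wilcoxon (150 − 136), before power falls below 80% on the stated inputs.

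**What to change.** - **9.7:** make the primary population all randomised patients in their allocated group. If patients who never reach anaesthetic induction are left out because the endpoint has no starting point, justify this by the blinding and report them by arm.
- **9.1:** analyse time to first significant stool by cumulative incidence, with death without transit as a competing event, and name the between-arm test in advance. State how living patients with no recorded stool are handled; 9.7 keeps them, but no rule covers them.
- **Sensitivity analyses:** a worst-rank Wilcoxon test, and the currently planned exclusion analysis with *early* defined by a fixed time limit. Report deaths by arm, with timing relative to transit recovery.
- **6.8:** delete the exclusion and replacement sentences and keep enrolment at 300.

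The direct cost is wording in 6.8, 9.1 and 9.7 and a little programming. There are three real downsides. The effect is no longer a plain mean difference in hours among patients with an observed time. A death imbalance unrelated to transit will also influence the result. Some power may be lost. The power figures above are for t and rank tests, so power for the cumulative-incidence test should be checked at 150 per group.

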4.2. Secondary Endpoints

Related to Secondary Objective 1 – Digestive Complications Rate:

- Intra-abdominal pressure measured via an adapted urinary catheter on Day 1 and Day 2 minimum, until measurement is feasible (cmH₂O)
- Vomiting
- Ogilvie syndrome defined by an occlusive syndrome >72h and cecal distension >8cm
- Mesenteric ischemia documented via abdominal imaging, colonoscopy, or laparoscopy
- Need for colonoscopy
- Placement of nasogastric tube
- Intolerance to solid food at Day 2

Related to Secondary Objective 2 – Respiratory Complications Rate:

- Duration (hours) of invasive and non-invasive mechanical ventilation (NIV, Optiflow)
- Reintubation
- Assisted ventilation (invasive or non-invasive) at Day 2
- Pneumonia, defined by a radiological infiltrate plus at least 2 criteria: T>38°C; leukocytosis or leukopenia; purulent secretions

Related to Secondary Objective 3 – Infectious Complications Rate:

- Septicemia defined by two positive blood cultures with the same organism within 48h (catheter or peripheral)
- Superficial or deep sternal infection (return to operating room for wound)

Related to Secondary Objective 4 – Pain Assessment:

- VAS (Visual Analog Scale) at Day 1, Day 2, and Day 3
- Total opioid consumption in morphine equivalent mg

Related to Secondary Objective 5:

- Total hospitalization duration in days

Related to Secondary Objective 6:

- Length of stay in intensive care unit and CCU in days

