9. STATISTICS

9.1. Statistical Methods

The analysis will proceed in 3 stages:

Descriptive Analysis:

Description of the total population and by group. For categorical variables: absolute and relative frequencies. For normally distributed continuous variables: mean and standard deviation. For non-normal distributions: median and interquartile range.

Inferential Analysis:

Comparisons between the 2 randomized groups will use chi-squared test for categorical variables; Student's t-test for Gaussian continuous variables; Wilcoxon-Mann-Whitney test for non-Gaussian variables. For pain scores over time, a mixed model for repeated measures will be used.

Exploratory Analysis:

Bivariate (correlation coefficients) or multivariate tests (multiple regression, logistic regression) to determine relationships between variables, including the effect of age, sex, and obesity (BMI>30).

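### As written, the mITT rule drops patients who die before a first stool from every analysis, so complications recorded before such a death leave the between-arm comparison

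*Combined protocol and SAP*

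**What the plan says.** Section 9.7 (Analysis Population) names one population, the mITT set: "all randomized patients excluding those who died early without bowel transit recovery (absence of primary endpoint". Patients are analysed in the arm to which they were randomised, and a CONSORT diagram is promised.

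Section 6.8 (Stopping Rules for Individual Participants) gives the same rule with its consequence: "Early death without bowel transit recovery (absence of primary endpoint) will lead to exclusion from analysis (mITT). These patients will be replaced". The purpose stated for replacement is to protect power. How early a death must be to count is not defined.

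Section 9.1 (Statistical Methods) sets the tests without naming another population: "Comparisons between the 2 randomized groups will use chi-squared test for categorical variables". Its descriptive stage promises "Description of the total population and by group".

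Section 4.2 (Secondary Endpoints) lists yes/no complications that can occur before an early death, among them reintubation, pneumonia, septicaemia and "Mesenteric ischemia documented via abdominal imaging, colonoscopy, or laparoscopy". Two further items are a status at a fixed day: "Intolerance to solid food at Day 2" and "Assisted ventilation (invasive or non-invasive) at Day 2".

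Section 6.2.4 collects vital status and adverse events daily in hospital and again at 1 month. Section 8.4 requires immediate notification of every fatal event, and also of Ogilvie syndrome, mesenteric ischaemia and perforation.

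**The concern.** A patient who dies without a stool has no value for the primary endpoint, and that is the reason given for the exclusion. The reason does not carry over to a complication already observed and recorded before the death. Because the exclusion is not tied to the primary analysis, following the text removes those complications from the chi-squared comparisons as well. Replacement then refills the arm, so the denominator looks complete.

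The exclusion also depends on something that happens after randomisation and that the drug is meant to change. If naloxegol shortens time to stool, a death at a given hour is more likely to come before the first stool on placebo than on naloxegol. The same death could then be kept in one arm and removed from the other. At stake is whether the secondary complication results compare all randomised patients.

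**Working it through.** **1. Scope of the rule.** Section 6.8 excludes from analysis without naming an endpoint. Section 9.7 defines the only set in the supplied text. Section 9.1 tests complications without naming a different set. Read together, the complications of excluded patients are not compared.

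**2. The plan's own figure.** Section 9.2 assumes "For a 15% reduction (48h to 41h) in the treated group, standard deviation of 20h", two-sided alpha 5% and power 80%. The usual formula gives 2 × (1.960 + 0.842)² × 20² / 7² = 128.1, so 129 per group and 258 in total. The stated 300 is not reproduced but errs on the large side: power is 0.858 at 150 per group. Without replacement it would still be 0.855 with 1% early deaths and 0.847 with 3% (assumed rates). The size of the trial is therefore not the issue here, and 150 per arm is used below.

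**3. Effect on one arm's rate.** The documents give no mortality or complication rate. Assume *d* = 0 to 3 deaths before a first stool in an arm (0% to 2% of 150), all replaced, each with one recorded complication, and 8 events among all randomised. The all-randomised rate is 8/(150 + *d*); the mITT rate is (8 − *d*)/150.

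| *d* | All randomised | mITT | Understatement (points) |
|---|---|---|---|
| 0 | 8/150 = 5.33% | 8/150 = 5.33% | 0 |
| 1 | 8/151 = 5.30% | 7/150 = 4.67% | 0.63 |
| 2 | 8/152 = 5.26% | 6/150 = 4.00% | 1.26 |
| 3 | 8/153 = 5.23% | 5/150 = 3.33% | 1.90 |

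The last column is an upper limit for each *d*, because every death is given an event.

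**4. How unequal the exclusion could be.** Take means of 48 h and 41 h and SD 20 h from 9.2, and assume that patients who die have the same stool times as the others. The chance of no stool yet at time *t*, placebo vs naloxegol, is:

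| *t* | Normal | Lognormal, same mean and SD |
|---|---|---|
| 24 h | 88% vs 80% | 94% vs 82% |
| 48 h | 50% vs 36% | 42% vs 28% |
| 72 h | 12% vs 6% | 11% vs 7% |

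The gap is widest at 48 h. With 3 deaths per arm at that hour, the expected numbers excluded are 3 × 0.500 = 1.50 vs 3 × 0.363 = 1.09 (Normal), or 1.26 vs 0.85 (lognormal): about 0.4 of a patient apart.

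**5. Effect on the between-arm difference, equal deaths.** Normal case, 8 events per arm among all randomised, every excluded death with an event:

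- mITT: 6.50/150 = 4.33% on placebo, 6.91/150 = 4.61% on naloxegol; difference 0.27 points.
- All randomised: 8/151.50 = 5.28% and 8/151.09 = 5.29%; difference about 0.01 points.

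The shift is about 0.3 points, and it makes naloxegol look slightly worse. The lognormal figures give the same: 6.74/150 = 4.49% and 7.15/150 = 4.77%. The standard error of a difference at a 5% rate is √(2 × 0.05 × 0.95/150) = 0.025, or about 2.5 points, so the shift is roughly a tenth of a standard error.

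**6. Unequal deaths.** The extreme within the assumed range is 3 excluded deaths in one arm and none in the other, each with an event. The mITT rates are 3.33% and 5.33% (2.00 points apart), against 5.23% and 5.33% in all randomised (0.10 apart), a shift of 1.9 points. Nothing in the documents suggests such an imbalance. If exclusions and their prior events are balanced, the difference does not move and both rates are merely understated.

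**The case against.** The strongest reply is that only the primary analysis was meant. Both sections give the missing primary endpoint as the reason, replacement is justified by power, and the only power calculation is for that endpoint. Section 9.1 speaks of the total population and of the randomised groups, not of the mITT set. This reading is possible. But the text does not state it, no all-randomised set is defined, and 6.8 excludes from analysis without qualification. If this was the intention, one sentence settles it.

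Second, the supplied text passes from 9.3 to 9.7 and from 8.1 to 8.4. Another set or a safety analysis could stand in the sections not supplied, so the point holds only for the text at hand.

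Third, the model for unequal exclusion is rough. Dying patients may mostly have no stool in either arm, which would make exclusion nearly equal. The 24 h figures apply the full 7 h benefit although only the 12.5 mg dose precedes the first postoperative tablet. The endpoint runs from anaesthetic induction, while the 48 h mean is counted postoperatively. These objections stand, and they are reasons not to rely on the 0.3 points as more than an order of magnitude.

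A reader might infer that deaths or serious complications are concealed. The documents do not support that: the CONSORT diagram and the notifications in 8.4 disclose the deaths, and 8.4 also covers mesenteric ischaemia and Ogilvie syndrome. What they do not do is return those events to a between-arm rate.

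**Conclusion.** The point holds as a defect in the stated rule, with a small expected effect. Followed as written, complications recorded before an early death without a stool are left out of the comparison of complication rates, for a reason that does not apply to them.

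The size rests on assumed deaths and events, since the documents give neither. With 0 to 3 such deaths per arm, one arm's rate is understated by 0 to 1.9 points, the top figure requiring an event in every such death. With equal deaths per arm, the between-arm difference moves by about 0.3 points against a standard error of about 2.5. Unequal deaths or prior events would move it more. With no such deaths the effect is nil.

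A reader might take 1.9 points as the bias in the treatment comparison. It is a shift in one arm's rate, and it becomes a shift in the difference only if all the excluded deaths fall in one arm. Nor does this point affect the primary conclusion.

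**What to change.** In 9.7, limit the early-death exclusion to the primary time-to-stool analysis, and align 6.8.

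Compare the binary event complications of 4.2 in all randomised patients, as randomised, including those who died and were replaced. The chi-squared test of 9.1 can stay. A patient who dies early without an event counts as event-free in this comparison, so report deaths to 1 month and the 8.4 events by arm as n/N beside it, to make such deaths visible.

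For the two Day 2 status endpoints (solid food and assisted ventilation), show deaths before Day 2 as a separate category by arm, and state that the test is among patients alive at Day 2. This is a deliberate exception to the all-randomised principle, because the status does not exist for a patient who has died.

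The cost is a few lines in 9.7, 6.8 and 9.1 and one extra table, from data already collected under 6.2.4. The sample size does not change. The downside is that denominators differ slightly from the primary analysis, for example 153 instead of 150 in an arm with three replaced deaths.
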